13.4. Reporting Adverse Events

The Investigator will notify the Sponsor of an adverse event by e-mail, facsimile, or telephone as soon as possible and no later than 24 hours from discovery for any serious /significant adverse events, and 2 days from discovery for any non-significant adverse event. In addition, a written report will be submitted by the Principal Investigator to the IEC/IRB according to their requirements (section 13.4.2). The report will comment whether the adverse event was considered to be related to the test article, study treatment or study procedures.

13.4.1. Reporting Adverse Events to Sponsor

Serious/Significant Adverse Events

The Investigator will inform the sponsor of all serious/significant adverse events occurring during the study period as soon as possible by e-mail or telephone, but no later than 24 hours following discovery of the event. The Investigator is obligated to pursue and obtain information requested by the Sponsor in addition to that information reported on the eCRF. All subjects experiencing a serious/significant adverse event must be followed up and all outcomes must be reported.

When medically necessary, the Investigator may break the randomization code to determine the identity of the treatment that the subject received. The Sponsor and study monitor should be notified prior to unmasking the test articles.

In the event of a serious/significant adverse event, the Investigator must:

- Notify the Sponsor immediately.
- Obtain and maintain in the subject's records all pertinent medical information and medical judgment for colleagues who assisted in the treatment and follow-up of the subject.
- Provide the Sponsor with a complete case history which includes a statement as to whether the event was or was not related to the use of the test article.
- Notify the IEC/IRB as required by the IEC/IRB reporting procedure according to national regulations.

Unanticipated (Serious) Adverse Device Effect (UADE)

In the event of an Unanticipated (Serious) Adverse Device Effect (UADE), the Investigator will submit a report of the UADE to the Sponsor and IEC/IRB as soon as possible, but no later than 24 hours after the Investigator first learns of the effect. This report is in addition to the immediate notification mentioned above.

The Sponsor must conduct an evaluation of the UADE and must report the results of the evaluation to FDA, the IEC/IRB and participating Investigators within 10 working days after the Sponsor first receives notification of the effect.

Non-Serious Adverse Events

All non-serious adverse events, including non-serious adverse device effects, will be reported to the sponsor by the Investigator no later than 2 days from discovery.

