13. ADVERSE EVENTS

13.1. Definitions and Classifications

Adverse Event (AE) – An AE is "any untoward medical occurrence, unintended disease or injury, or untoward clinical signs (including abnormal laboratory findings) in subjects, users or other persons, whether or not related to the investigational medical device." Note: This definition includes events related to the investigational medical device or the comparator, and to the procedures involved. For users or other persons, this definition is restricted to events related to investigational medical devices.¹

An AE includes any condition (including a pre-existing condition) that:

- 1. Was not present prior to the study, but appeared or reappeared following initiation of the study.
- 2. Was present prior to the study but worsened during the study. This would include any condition resulting from concomitant illnesses, reactions to concomitant medications, or progression of disease states.

Note: Pregnancy must be documented as an adverse event and must be reported to the clinical monitor and to the Sponsor immediately upon learning of the event.

Serious Adverse Event (SAE) – An SAE is any adverse event that led to any of the following:

- Death
- Serious deterioration in the health of the subject that resulted in any of the following:
- Life-threatening illness or injury
- Permanent or persistent impairment of a body structure or a body function
- Hospitalization or prolongation of patient hospitalization

- Medical or surgical intervention to prevent life-threatening illness or injury or permanent impairment to a body structure or a body function.
- Chronic disease
- Foetal distress, foetal death or a congenital physical or mental impairment of birth defect.

Diagnoses and conditions that are considered Ocular Serious Adverse Events include, but not limited to:

- Microbial Keratitis (MK)
- Iritis (including cells in the anterior chamber)
- Permanent decrease in best spectacle corrected visual acuity equivalent to 2 acuity lines or greater
- Central Corneal Opacity
- Central Corneal Neovascularization
- Uveitis
- Endophthalmitis
- Hypopyon
- Hyphemia
- Penetration of Bowman's Membrane
- Persistent Epithelial Defect
- Limbal cell Damage leading to Conjunctivalization

Significant Adverse Events – are defined as events that are symptomatic and warrant discontinuation (temporary or permanent) of the contact lens wear

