Diagnoses and conditions that are considered Ocular Significant Adverse Events include, but not limited to the following:

- Contact Lens Induced Peripheral Ulcer (CLPU)
- Significant Infiltrative Events (SIE)
- Superior Epithelial Arcuate Lesions (SEALs)
- Any Temporary Loss of > 2 Lines of BSCVA
- Other grade 3 or higher corneal findings, such as abrasions or edema
- Non-contact lens related corneal events e.g. Epidemic Keratoconjunctivitis (EKC)
- Asymptomatic Corneal Scar
- Any corneal event which necessitates temporary lens discontinuation > 2 weeks

Non-Significant Adverse Events – are defined as those events that are usually asymptomatic and usually do not warrant discontinuation of contact lens wear but may cause a reduction in wear time. However, the Investigator may choose to prescribe treatment as a precautionary measure.

Diagnoses and conditions that are considered Ocular Non-Significant Adverse Events include, but not limited to the following:

• Non-significant Infiltrative Event (NSIE)

- Contact Lens Papillary Conjunctivitis (CLPC)
- Superficial Punctate Keratitis (SPK)
- Conjunctivitis: Bacterial, Viral, Allergic
- Blepharitis
- Meibomianitis
- Contact Dermatitis
- Localized Allergic Reactions
- Any corneal event not explicitly defined as serious or significant adverse event, which necessitates temporary lens discontinuation < 2 weeks

Adverse Device Effect (ADE) – An ADE is an "adverse event related to the use of an investigational medical device."

NOTE 1: This definition includes adverse events resulting from insufficient or inadequate instructions for use, deployment, implantation, installation, or operation, or any malfunction of the investigational medical device.

NOTE 2: This definition includes any event resulting from use error or from intentional misuse of the investigational medical device.⁷

Unanticipated Adverse Device Effect (UADE) – A UADE is any serious adverse effect on health or safety or any life-threatening problem or death caused by, or associated with, the test article, if that effect, problem, or death was not previously identified in nature, severity, or degree of incidence in the investigational plan, Investigator's Brochure or protocol, or any other unanticipated serious problem associated with the test article that relates to the rights, safety and welfare of subjects.

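### The closing paragraph of 13.4.1 gives every non-serious event 2 days, which takes in Significant events that 13.4 and the opening of 13.4.1 require within 24 hours

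*Combined protocol and SAP*

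**What the plan says.** Protocol section 13.1 defines three classes. Serious rests on outcome criteria plus a list of named ocular conditions. Significant is a separate class: "events that are symptomatic and warrant discontinuation (temporary or permanent) of the contact lens wear", with its own ocular list. Non-Significant is the third.

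Section 13.4 sets the general reporting rule. Serious and significant events share a 24-hour limit, and the longer limit is "2 days from discovery for any non-significant adverse event".

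Section 13.4.1 then gives the detail. Its opening block covers all serious and significant events, sets the limit at "no later than 24 hours following discovery of the event", and adds the instruction "Notify the Sponsor immediately". Its closing paragraph, headed for non-serious events, reads: "All non-serious adverse events, including non-serious adverse device effects, will be reported to the sponsor by the Investigator no later than 2 days" from discovery.

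**The concern.** The reporting rule runs along one axis in 13.4 and in the opening of 13.4.1 (significant or not), and along another in the closing paragraph of 13.4.1 (serious or not). The two axes would agree only if every Significant event were also Serious, and 13.1 does not make it so. The wide word *All* in the closing paragraph then pulls the middle class into the 2-day limit.

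Timely sponsor notice of corneal events that stop lens wear is what is at stake. Such events can arise from routine procedures in this trial. Slit-lamp examination is done at every visit, a Grade 3 finding at Visit 2 or 3 is recorded as an adverse event, and corneal findings of Grade 3 or above are on the Significant list. The shortest washout is 2 days, so an event found at Visit 2 and reported at the 2-day limit could reach the sponsor only when the second lens is due to be dispensed. The protocol is also multi-site, so sites could read the deadline differently, and a site reporting at, say, 40 hours could point to protocol text in its support.

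**Working it through.** No statistic is involved. The check is a comparison of texts, one count and one subtraction.

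**Step 1. Is there a class that is Significant but not Serious?** The inputs are the two ocular lists in 13.1. The Serious list has 12 items and the Significant list has 8. Items of the Significant list that are named on the Serious list: 0 of 8. All 8 can therefore be Significant without being Serious, provided the particular case meets none of the SAE outcome criteria.

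**Step 2. The three limits side by side.**

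| Place | Events covered | Limit |
|---|---|---|
| 13.4 | serious or significant | 24 hours |
| 13.4 | non-significant | 2 days |
| 13.4.1, opening block | all serious or significant | 24 hours |
| 13.4.1, closing paragraph | all non-serious | 2 days |

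**Step 3. Apply them to one case.** Take a CLPU that meets no SAE criterion. It is named as Significant, so 13.4 gives 24 hours and the opening block of 13.4.1 gives 24 hours. It is not Serious, so the closing paragraph gives 2 days. SIE and SEALs come out the same way.

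**Step 4. Size of the gap.** 2 days = 48 hours, and 48 − 24 = 24 hours.

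**Step 5. Which limit is intended?** Section 13.4 divides events into two groups and assigns the 2-day limit to the non-significant group. The closing paragraph gives the same 2 days, so it reads as the detailed version of that second group under the wrong label. Replacing non-serious with non-significant brings all four rows of the table into agreement.

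**Step 6. What the sentence does not touch.** It sets a deadline and nothing else. The other duties in the opening block remain attached to Significant events whatever the closing paragraph says: "Provide the Sponsor with a complete case history", and "All subjects experiencing a serious/significant adverse event must be followed up and all outcomes must be reported".

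**The case against.** The strongest reply is that nothing truly conflicts. Both limits are maxima, and a report within 24 hours satisfies each. The 24-hour duty appears twice and is reinforced by the call for immediate notice. Read in order, the closing paragraph is simply the residual class under a loose heading, so a site reporting a CLPU at 2 days would breach the more specific text. Most of this stands, and it limits the size of the point. It does not remove it: no sentence says that the specific rule prevails, and the closing paragraph has no exception.

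A reader might go further and infer that 13.1 itself is defective. It names conditions such as SPK and conjunctivitis as Non-Significant even though a given case may be symptomatic and stop lens wear, and a reader might want a tie-break making the Significant definition override the list. The documents do not support that step. The Non-Significant list does carry precedence wording: its corneal catch-all yields to anything explicitly classed as serious or significant. That wording does not reach named non-corneal diagnoses, but 13.2 gives classification of each case to the investigator together with the medical monitor. The tie-break would also largely empty the Non-Significant item for corneal stops shorter than 2 weeks. It could add withdrawals under 8.2, where a significant event that stops wear for four or more days ends participation. Where to draw that line is a clinical choice for the sponsor.

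Section 1.5 might also be read as evidence of harm, since earlier studies of these lenses recorded no serious event and one significant one. That event predated enrollment, was stable at the final evaluation and was judged unrelated. Nothing shows that it was reported late or under this wording, and no denominator is given.

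**Conclusion.** The inconsistency is real and worth correcting, but small. Read literally, the closing paragraph of 13.4.1 allows 2 days for Significant events that are not SAEs, against 24 hours elsewhere. The consequence is at most one day in sponsor notification for that class. It would be tempting to say that the protocol permits late reporting of significant events. It does not go that far: the stray sentence weakens the 24-hour rule without cancelling it. Exposure of the second lens period is limited too, because 8.2 withdraws subjects with a corneal infiltrative event and those whose significant event stops wear for four or more days, although this does not cover every Significant event. The primary visual acuity analysis and the sample size are unaffected.

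The conclusion assumes that the event in question meets no SAE criterion, and that 13.4 expresses the sponsor's intent. How often such events will occur cannot be estimated from the documents.

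**What to change.** In the closing paragraph of 13.4.1, change the heading from Non-Serious to Non-Significant Adverse Events. In the sentence below it, replace non-serious with non-significant in both places, and add in parentheses after the first that this means neither Serious nor Significant. Keep the limit of 2 days from discovery. Sections 13.1 and 13.4 need no change for this purpose.

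The cost is one heading, one sentence and the matching line in the adverse-event eCRF guide. The only practical effect is that a site relying on the present sentence would report a Significant, non-serious event up to one day sooner, as 13.4 already requires.

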13.4.2. Reporting Adverse Events to the Responsible IEC/IRB and Health Authorities

Adverse events that meet the IEC/IRB requirements for reporting must be reported within the IEC/IRB's written guidelines. Each clinical site will refer to and follow any guidelines set forth by their Approving IEC/IRB. Each clinical site will refer to and follow any guidelines set forth by their local governing Health Authorities.

The Sponsor will report applicable Adverse Events to the local health authorities according to the written guidelines, including reporting timelines.

13.5. Event of Special Interest

Not applicable

13.6. Reporting of Pregnancy

Subjects reporting pregnancy (by self-report) during the study will be discontinued after the event is recorded as an Adverse Event. Once discontinued, pregnant participants and their fetuses will not be monitored for study related purposes. Pregnant participants are not discontinued from contact lens or solution related studies for safety concerns, but due to general concerns relating to pregnancy and contact lens use. Specifically, pregnant women are discontinued due to fluctuations in refractive error and/or visual acuity that occur secondary to systemic hormonal changes, and not due to unforeseen health risks to the mother or fetus.

14. STATISTICAL METHODS

14.1. General Considerations

Statistical Analysis will be undertaken by the sponsor or under the authority of the sponsor. A general description of the statistical methods to be implemented in this clinical trial is outlined below.

All data summaries and statistical analyses will be performed using the SAS software Version 9.4 or higher (SAS Institute, Cary, NC).⁶ Throughout the analysis of data, the results for each subject/eye will be used when available for summarization and statistical analysis. Unscheduled visits will be summarized separately and will be excluded from the statistical analysis.

Summary tables (descriptive statistics and/or frequency tables) will be provided by lens type (Test and Control (1-Day Acuvue Define Fresh Honey), timepoint (Baseline, Fitting Evaluation, Lens Dispensing, 1-Week Follow-up), and analysis population (ITT, PP or safety), as appropriate. Continuous variables will be summarized with descriptive statistics (n, mean, standard deviation (SD), median, minimum and maximum). Frequency count and percentage of subjects or eyes within each category will be provided for categorical data.

14.2. Sample Size Justification

This study was designed and powered to test that the proportion of eyes with distance high luminance high contrast logMAR visual acuity less than 0.176 logMAR VA is superior to 0.90. Clinical study was used in the sample size calculation since this historical study also collected distance monocular HLHC logMAR VA post-lens fitting and utilized the same study design. Moreover, the 1-Day Acuvue Define FRESH GREEN lenses evaluated in are a part of the portfolio for 1-DAY Acuvue Define with Lacreon (Product Health & Safety Clinical Risk Assessment⁹). Furthermore, all 1-Day Acuvue Define with Lacreon products utilize the same contact lens design (1997), lens material (etafilcon A), and manufacturing processes, and specifications for lens mechanical and optical parameters (1997).

. Table 7 below displays full details regarding visual acuity data for

Table 7:Distance Monocular High Luminance High Contrast logMAR Visual Acuity- Fitting Evaluation - ITT Population

	Fresh Green – Pilot Line (Test) N= 112	Fresh Green – Line 26 (Control) N=110
logMAR VA		
Mean (SD)	-0.0471(0.08531)	-0.0495(0.08283)
Median	-0.0400	-0.0600
Min - Max	-0.3000 - 0.2400	-0.2600 - 0.1600
logMAR VA < 0.176 n(%)		
Yes	111 (99.1)	110 (100.0)
No	1 (0.9)	0 (0.0)
Total	112	110

N=Total number of eyes.

SD: Standard Deviation, Min: Minimum, Max: Maximum

14.3. Analysis Populations

Safety Population:

All subjects who are administered any test article excluding subjects who drop out prior to administering any test article. At least one observation should be recorded.

Per-Protocol Population:

All subjects who successfully complete all visits and do not substantially deviate from the protocol as determined by the trial cohort review committee prior to database hard lock. Justification for the exclusion of subjects with protocol deviations from the per-protocol population set will be documented in a memo to file.

Intent-to-Treat (ITT) Population:

All randomized subjects regardless of actual treatment and subsequent withdrawal from the study or deviation from the protocol. At least one observation should be recorded.

14.4. Level of Statistical Significance

The planned primary analysis for this study will be conducted with an overall type I error rate of 5%.

14.5. Primary Analysis

The primary analysis will be conducted on the ITT population.

Visual Acuity (logMAR)

Distance monocular high luminance high contrast logMAR VA scores post-fitting will be converted into a binary response for the purposes of analysis. YY=1 if an eye has logMAR VA less than 0.176 and YY=0 otherwise. The dichotomized variable YY will be analyzed using a Bayesian beta-binomial model for correlated binary data⁹.

The Model:

Let Y_1 and Y_2 denote the binary outcomes of logMAR VA less than 0.176 (Yes/No) in left and right eyes, respectively, post-fitting for the Test lens. Considering the correlation, ρ , between Y_1 and Y_2 , the distribution of the sum $Y = Y_1 + Y_2$ is obtained by the mixture of two variables. One of them follow a binomial distribution Bin(2, p) with mixing probability $(1 - \rho)$ and the other one follows a modified Bernoulli distribution, MBern(p), taking value 0 and 2 rather than conventional 0 and 1, with mixing probability ρ :

$$P(Y = y | p, \rho) = (1 - \rho)Bin(2, p)I_{A1} + \rho MBern(p)I_{A2}$$
,

where $I_{A1} = \{0, 1, 2\}, I_{A2} = \{0, 2\}$ and p is the probability of success (i.e., acceptable lens fitting).

To overcome the complexity of the mixture likelihood a latent variable Z_i , i = 1, 2 is introduced in the model to indicate in which component of the model the observation y_i , i=1, 2, belongs to, that is,

 $Z_i = \begin{cases} 1, \text{ if the observation belong to the MBern(p),} \\ 0, \text{ if the observation belong to the Bin(2, p)} \end{cases}$

The joint distribution of the augmented data (Y_i, Z_i) , i = 1, 2, is given by

$$\begin{split} P(Y = y_i, Z = z_i | p, \rho) \\ &= \rho^{z_i} p^{y_i z_i/2} (1-p)^{(2-y_i) z_i/2} (1-\rho)^{1-z_i} {2 \choose y_i} p^{y_i(1-z_i)} (1-p)^{(2-y_i)(1-z_i)} \end{split}$$

The probability p links to the regression variables through a logit transformation as follow:

logit (p) =
$$\beta_0 + \beta_1$$
lens

It is assumed that β_0 , β_1 and ρ to be independent with a non-informative prior N(0, 1000) for β_0 and β_1 , and beta(0.5, 0.5) for ρ . The Metropolis sampler algorithm as implemented in the SAS/STAT MCMC procedure will be used to estimate the posterior distributions of the parameters (β_0 , β_1 , ρ). Inferences will be made based on a posterior credible interval for the relevant parameters.

Bayesian Estimation and Statistical Evaluation of Hypothesis:

Superiority of the Test lens relative to the pre-defined threshold with respect to the proportion of eyes with logMAR VA less than 0.176 will be evaluated using Bayesian statistics.

Primary Hypothesis

The null and alternative hypothesis to test for superiority are as follows:

$$H_o: P_T \leq 0.90$$

$H_A: P_T > 0.90$

Where P_T is the probability of the event (i.e., the probability of having logMAR VA < 0.176 in on eye while wearing the Test lens). Based on the central posterior probability distribution of the proportion p_T , superiority is interpreted as 95% probability of the Test lens being statistically higher than the pre-specified threshold of 0.90 (i.e., $P_T > 0.90$). If the lower bound of the 95% central posterior credible interval is above 0.90, it can be concluded that there is a 95% probability that the P_T is superior to 0.90 (statistically higher) based on the observed sample (i.e., $P(p_{Test} > 0.90) \ge 0.975$).

In the case of all eyes have a logMAR VA less than 0.176 (i.e., zero events of logMAR VA 0.176 or higher), a Bayesian hierarchical model accounting for zero event problem will be considered¹⁰.

14.6. Secondary Analysis

Not applicable.

14.7. Other Exploratory Analysis

Not applicable.

14.8. Interim Analysis

No interim read will be conducted.

14.9. Procedure for Handling Missing Data and Drop-Outs

Missing or spurious values will not be imputed. The count of missing values will be included in the summary tables and listings.

14.10. Procedure for Reporting Deviations from Statistical Plan

The analysis will be conducted according to that specified in above sections. There are no known reasons for which it is planned to deviate from these analysis methods. If for any reason a change is made, the change will be documented in the study report along with a justification for the change.

